### **6.4 Post-Participation Confirmation**

After the participants have completed their scheduled visits, (barring earlier termination), they will have successfully completed the study.

### **6.5 Photographs**

During the consenting process, participants will be asked if they agree to have photos of their incision sites taken. Only photos of the incision and product application sites will be taken, no other surrounding patient identifiers will be included (i.e. birthmarks, tattoos, any dermatologic identifiers such as scars, etc.). As the study progress the quantity and quality of photos will be reviewed until it is deemed a sufficient variety of comparative photographs between products and application site/groups has been taken. This process will allow for an appropriate representation of photos to be gathered without requiring every single patient enrolled to have incisional site photos. This will also allow the participants to continue study enrollment despite opting not to have incisional site photos taken. None of the photographs will be used for statistical comparison.

## 7 ADVERSE DEVICE EVENTS (ADEs)

### 7.1 Definition of ADE

The ADE is the adverse event related to the use of an investigational medical apparatus resulting from insufficiencies or inadequacies in the instructions for use, the deployment, installation, the operation, or any malfunction of the investigational medical device or from error use.

### 7.2 Definition of Serious Adverse Event (SAE) / Serious Adverse Device Event (SADE)

The SADE is the adverse device effect that has resulted in any of the consequences characteristic of a serious adverse event (SAE), such as:

- Death
- A life-threatening adverse event
- Inpatient hospitalization or prolongation of existing hospitalization
- A persistent or significant incapacity or substantial disruption of the ability to conduct normal life functions or,
- A congenital anomaly/birth defect.

Important medical events that may not result in death, be life-threatening, or require hospitalization may be considered serious when, based upon appropriate medical judgment, they may jeopardize the participant and may require medical or surgical intervention to prevent one of the outcomes listed in this definition. All SADE will be reported to the reviewing IRB as necessary according to their rules.

### 7.3 Definition of Unanticipated Adverse Device Effect (UADE)

Any serious adverse effect on health or safety or any life-threatening problem or death caused by, or associated with, a device, if that effect, problem, or death was not previously identified in nature, severity, or degree of incidence in the investigational plan or application (including a supplementary plan or application), or any other unanticipated serious problem associated with a device that relates to the rights, safety, or welfare of subjects.

### 7.4. Severity of ADE

- **Grade 1:** Mild; asymptomatic or mild symptoms; clinical or diagnostic observation only; intervention not indicated.
- **Grade 2:** Moderate; minimal, local or noninvasive intervention indicated; limited age-appropriate instrumental activities of daily living.

- **Grade 3:** Severe or medically significant but not immediately life-threatening; hospitalization or prolongation of hospitalization indicated; disabling; limiting activities of daily living involving self-care.
- **Grade 4:** Life threatening consequences; urgent intervention indicated.
- **Grade 5:** Death related to ADE.

### 7.5 Relatedness of ADE and SADE

- **Unrelated:** This category applies to those ADEs / SADEs which, after careful consideration, are clearly and incontrovertibly due to extraneous causes (disease, environment, etc.)
- **Possible:** This category applies to those ADEs / SADEs for which, after careful medical consideration at the time they are evaluated, a connection with the Investigational Product administration appears unlikely but cannot be ruled out with certainty.
- **Probable:** This category applies to those ADEs / SADEs which, after careful medical consideration at the time they are evaluated, are felt with a high degree of certainty to be related to the Investigational Product.
- **Definite:** This category applies to those ADEs / SADEs which, after careful consideration, are clearly and incontrovertibly due to the Investigational Product.

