### **6.3 Follow-up post-operative visit (Visit 2 & 3)**

In the second and third post-operative visits, the incisional wounds will be assessed for possible dehiscence and the results will be recorded. Moreover, an incisional site cosmetic score will be obtained using the Modified Hollander score for linear scars and will be used to further assess and categorize the current wound state. As with the first visit, the research staff will also assess any potential adverse event that may have resulted from the use of the topical adhesives. Additionally, any incidence of surgical site infections will be noted. Following the assessments during the third visit, the participants will be dismissed from the study. The CDC SSI and ICDRG grading systems will be used if either of the two events are deemed applicable by the study staff.

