### **8.2 Randomization**

The order of products tested first or second will be randomly assigned according to a randomization table developed by the biostatistics team. We will conduct a two-arm, prospective, unblinded, randomized prospective control trial by which participants will be randomly assigned to either receive treatment A: the Dermabond wound closure adhesive or the treatment B: OptiClose wound closure adhesive in participants undergoing the closure of any subcutaneous tissue following surgical site incisions. After assignment to treatment arm per incisional length requirements, participants will be randomized using

simple randomization, with 15 participants designated to receive Opticlose and 15 to receive Dermabond. Participants will be patients undergoing a skin closure of a full thickness surgical incision. For the products tested in this study, a total of 60 participants will be required to complete the study, 30 in each incisional length group. If a participant is unable to complete the study, the participant will be replaced such that the new participant will be assigned to the randomization cohort of the replaced participant.

Enrollment will continue until the study from the evaluable number of participants (60) is completed.

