#### **8.8.4 Adverse Device Events**

All adverse device events will be included in the analyses and report documents, including but not limited to skin irritation, redness, and itching.

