## 9.2. Abbreviations

ADE	Adverse Device Event
UADE	Unanticipated Adverse Device Effect
SADE	Serious Adverse Device Event
ICDRG	The International Contact Dermatitis Research Group
CFR	Code of Federal Regulations
CRA	Clinical Research Associate
CRF	Case Report Form
CRO	Contract Research Organization
FDA	Food and Drug Administration
GCP	Good Clinical Practice
GDP	Good Documentation Practice
HIPAA	Health Insurance Portability and Accountability Act
ICF	Informed Consent Form
ICH	International Conference on Harmonization
IRB	Institutional Review Board
ITT	Intent to Treat
LP	Limited Partnership
PI	Principal Investigator
PSF	Participant Screening Form
SAE	Serious Adverse Device Events
SSI	Surgical Site Infection
SOA	Schedule of Activities
U.S.	United States

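### Outside a few named endpoints, adverse events are reported only as device-related events judged by unblinded staff, and sections 7.1 and 7.5 conflict on whether unrelated events are collected

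*Combined protocol and SAP*

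**What the plan says.** Section 7.1 makes relatedness part of the definition: "The ADE is the adverse event related to the use of an investigational medical apparatus". At the two follow-up visits, under section 6.3, "the research staff will also assess any potential adverse event that may have resulted from the use of the topical adhesives". Section 8.8.4 states that "All adverse device events will be included in the analyses and report documents". It names no between-product test. Section 8.7 asks for summary tables with one column per treatment. Section 8.2 describes a "two-arm, prospective, unblinded, randomized prospective control trial", section 9.1.2 gives the safety determinations to the principal investigator, and section 8.3 plans no safety population.

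Section 7.5 grades ADEs and serious ADEs as Unrelated, Possible, Probable or Definite. Possible applies when "a connection with the Investigational Product administration appears unlikely but cannot be ruled out with certainty". Probable, the next level, applies to events that "are felt with a high degree of certainty to be related to the Investigational Product".

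Three safety-relevant outcomes have their own planned comparison by product: dehiscence or re-approximation (section 8.8.1), and surgical site infection and ICDRG-graded inflammatory reactions (section 8.8.2).

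**The concern.** A randomised comparison of adverse events is protected only if events are counted in the same way in both arms. Here an event outside the named endpoints counts once someone who knows which adhesive was used links it to that adhesive. If staff link local events more readily to one product, the ADE columns can differ when the true rates are equal, or match when the true rates differ. Redness, swelling or blistering round a fresh incision is the kind of event for which adhesive, skin preparation and surgery are all plausible causes, so attribution has room to vary.

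The conflict between 7.1 and 7.5 adds a second problem. Two people following the protocol in good faith could collect different sets of events, one leaving out what looks unrelated and the other recording it and grading it Unrelated. The published ADE count would then depend on which reading was used.

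**Working it through.** The documents state no safety figure, so there is nothing to reproduce. The check is mainly textual.

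**Step 1: routes by which an event reaches the analysis.**

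| Outcome | Where | Does entry depend on judged cause? |
|---|---|---|
| Dehiscence or re-approximation | 8.8.1 | No |
| Surgical site infection within 30 days | 8.8.2 | No relatedness condition, although 6.3 leaves use of the CDC criteria to staff judgement |
| ICDRG reaction | 8.8.2, with 6.2 and 6.3 | Partly: grading follows when staff detect an allergic reaction or consider the grading applicable |
| Any other adverse event | 7.1, 6.3, 8.8.4 | Yes, on the definition in 7.1 |

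Only the last row rests wholly on attribution. The third does so in part: redness that staff put down to surgery may never be graded.

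**Step 2: 7.1 against 7.5.** Under 7.1 an event must be related to be an ADE. Under 7.5 an ADE may be Unrelated. Both cannot hold. Either the Unrelated level is empty, or ADE is being used for any recorded event and 7.1 is wrong. No section settles which.

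**Step 3: the steps of the scale.** Moving up from Possible, the wording goes from a link that looks improbable to one held with strong certainty. An event with equally plausible causes fits neither. No section uses the levels to include, exclude or compare events, so this gap changes no planned result.

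**Step 4: how attribution could act (assumed inputs only).** Let the true event rate r be the same for both products, and let staff attribute a share a₁ of events to one product and a₂ to the other. Expected ADEs are n × r × a, and the apparent difference is r × (a₂ − a₁). Section 8.2 puts 15 per product in each of two incision-length groups, so n = 30 per product.

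| r | Shares 0.5 v 0.5 | Shares 0.5 v 0.8 | Shares 0.3 v 0.9 |
|---|---|---|---|
| 10% | 1.5 v 1.5 (0 points) | 1.5 v 2.4 (3 points) | 0.9 v 2.7 (6 points) |
| 20% | 3.0 v 3.0 (0 points) | 3.0 v 4.8 (6 points) | 1.8 v 5.4 (12 points) |
| 40% | 6.0 v 6.0 (0 points) | 6.0 v 9.6 (12 points) | 3.6 v 10.8 (24 points) |

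For example, 30 × 0.20 × 0.80 = 4.8 and 30 × 0.20 × 0.50 = 3.0; 1.8/30 = 6 points. The masking case: with shares of 0.80 and 0.50, true rates of 20% and 32% both give a recorded rate of 16% (0.20 × 0.80 = 0.32 × 0.50 = 0.16). The assumed range thus runs from no distortion to 24 points. It shows the mechanism and estimates nothing.

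**The case against.** The strongest reply is that most of what matters here is already compared without a causality judgement. Infection and dehiscence are counted whatever the cause. The Modified Hollander form, scored at both follow-ups, also records margin separation and swelling or infection for each wound. Section 8.8.1 mentions a test on adverse events rather than ADEs. This largely stands, and it rules out a reading that a reader might infer: that the whole safety comparison passes through attribution. The documents do not support that. The sentence in 8.8.1 does not close the remaining gap, because it sits under the primary endpoint and no section sets up collection of events regardless of cause.

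A reader might also infer that the faulty scale in 7.5 filters the events. It does not. Section 8.8.4 takes in all ADEs with no cut by level, so any filter lies in the definition in 7.1.

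Nor is it certain that the filter operates. The Unrelated level, the mention of AE alongside ADE in 7.6 and the separate SAE form in 7.8 fit a reading in which everything is logged and then graded. That is fair, and it is why the point is partly a contradiction to resolve. The expansion of SAE in section 9.2 as "Serious Adverse Device Events" should not be used as evidence of a filter: the heading of 7.2 gives the usual expansion, so 9.2 looks like a glossary slip.

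Two further replies stand. No passage suggests that attribution differs between products, and the illustrative gap is small against chance. For 16% v 10% with 30 per product, the standard error is √(0.16 × 0.84/30 + 0.10 × 0.90/30) = √0.00748, or about 8.6 points, so a 6-point gap would be unremarkable. And recording all events with the same unblinded staff would remove attribution but not detection bias.

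**Conclusion.** The point holds in a limited form. Outside infection and dehiscence, and with ICDRG reactions as a partial exception, adverse events enter the analysis and report as ADEs. On the definition in 7.1, that makes their tabulation by product depend on unblinded attribution. Although 8.8.4 names no test, tables laid out with a column per treatment under 8.7 would place the ADE counts side by side, and they would be read as a comparison.

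Sections 7.1 and 7.5 contradict each other, so whether unrelated events are collected is unknown. The missing middle of the scale is a real but lesser drafting defect, and correcting it alone would change no result.

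The size of any bias cannot be derived from the documents. It could be nil if attribution is even or if staff record everything. The point is worth acting on because the remedy is cheap and would take attribution out of the remaining safety tabulation, not because a distortion has been shown.

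**What to change.** - **Sections 6.3, 7.1 and 8.8.4:** require recording of every adverse event at or near the incision, and every serious adverse event, for both products whatever the judged cause. Tabulate them by randomised product, with relatedness as a descriptive column.
- **Sections 7.1 and 7.5:** reconcile them so that the relatedness scale applies to adverse events, with ADEs as the subset judged related. Add a level for a reasonable possibility where other causes are equally plausible, separate from a level for an unlikely link.
- **Section 9.2:** align the expansion of SAE with the heading of 7.2.

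The cost is protocol and case report form wording, a modest number of extra events to record and one more table. No extra visits or staff are needed. Section 8.1 already speaks of results, so collection may be complete. If so, tabulate every event that was recorded, by randomised product, and state in the report that collection may have been restricted to events judged device-related.

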### 7.6 Expectedness

The PI will be responsible for determining whether an ADE or SADE is expected or unexpected. An AE / ADE will be considered unexpected if the nature, severity, or frequency of the event is not consistent with the risk information previously described for the study intervention.

### 7.7 ADE Reporting

Non-serious ADEs are to be reported to the IRB per IRB reporting requirements.

### 7.8 SADE/UADE reporting

The SADEs will be recorded on the SADE/UADE form (provided by Medline Industries, LP.) by the study personnel and reviewed by the PI. The study personnel or the PI shall submit the completed SADE/UADE form to Medline as soon as possible, but in no event later than 48 hours after the PI first learns of the effect. The study personnel or the PI will be responsible for reporting the event to the IRB per the IRB's reporting requirements, and to the FDA if applicable. Thereafter, the study personnel or the PI shall submit additional reports concerning the effect as the FDA requests.

The PI shall complete a SAE Form no later than 48 hours after the investigator first learns of the effect. The PI shall report the SAE / SADE to the reviewing IRB, if applicable, according to their reporting requirements. The PI, who is responsible for conducting an evaluation of the SAE / SADE, shall report the results of such evaluation to the FDA and to all reviewing IRBs if applicable within 10 working days. Thereafter, the PI shall submit such additional reports concerning the effect as FDA requests.

For questions regarding this process or the event, you may contact your Medline clinical designee or the Clinical Research Scientist:

Name: [name]

[contact]

E-mail: [[contact]](mailto:[contact])

## **8 STATISTICAL CONSIDERATIONS**

### **8.1. Sample Size Determination**

The purpose of this study is to show non-inferiority between the two products. We are reporting superiority results, as the noninferiority results were indeterminate. A sample size of 30 per incisional length group was estimated based on the secondary outcome of difference in mean “Dry Time” using estimated means (no standard deviations) from the vendor for both OptiClose and Competitor product, and estimation of effect size. The comparison will be made using a one-sided, two-sample unequal-variance t-test, with a Type I error rate ( $\alpha$ ) of 0.025. The standard deviation for Group 1 is assumed to be 0.01 and the standard deviation for Group 2 is assumed to be 0.01. With sample sizes of 15 in OptiClose Product and 15 in Dermabond, and with 90% power, the corresponding detectable difference in means is 0.02226. Provided exact standard deviations, an exact difference can be adjusted accordingly. The detectable difference was computed using PASS 2024, version 24.0.2.

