### **8.7 Statistical Analysis of Study Endpoints**

Statistical analyses will be conducted in SAS® software, Version 9.4 or higher of the SAS System for Windows (Copyright © 2013 SAS Institute Inc.) or other appropriate statistical software.

All continuous variables will be summarized using the following descriptive statistics: n (non-missing sample size), mean, standard deviation, median, maximum and minimum. The frequency and percentages (based on the non-missing sample size) of observed levels will be reported for all categorical measures. In general, all data will be listed, sorted by site, treatment and subject, and when appropriate by visit number within subject. All summary tables will be structured with a column for each treatment in the order (Control, Experimental) and will be annotated with the total population size relevant to that table/treatment, including any missing observations. 95% confidence intervals will be calculated for all means.

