### **8.8.1 Primary Endpoint**

Incidence of wound edge apposition without dehiscence or need of re-approximation following wound closure.

Counts will be collected of participants not requiring wound re-approximation for both Opticlose and Dermabond. A Chi-Square test will be used to compare the observed frequencies of adverse events between the two products. The test statistic is calculated by comparing the observed frequency to the expected frequency under the null hypothesis. The p-value will be obtained to determine the statistical significance of the observed difference.

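### Section 8.1 sets a non-inferiority purpose and then reports superiority, while the plan gives no margin and judges the primary endpoint only by a p-value for a difference

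*Combined protocol and SAP*

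**What the plan says.** All references are to the combined protocol and SAP.

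- **8.1, purpose:** "The purpose of this study is to show non-inferiority between the two products". The next sentence reads: "We are reporting superiority results, as the noninferiority results were indeterminate".
- **8.1, sizing:** "A sample size of 30 per incisional length group was estimated based on the secondary outcome of difference in mean" dry time, using a "one-sided, two-sample unequal-variance t-test" at alpha 0.025 with 90% power and 15 per product in each incision-length group.
- **8.8.1, primary endpoint:** "Incidence of wound edge apposition without dehiscence or need of re-approximation following wound closure". This is a yes/no outcome.
- **8.8.1, primary test:** "A Chi-Square test will be used to compare the observed frequencies of adverse events between the two products". The decision rule is: "The p-value will be obtained to determine the statistical significance of the observed difference". The section does not say whether the two length groups are pooled, and it names adverse events rather than the apposition counts as what is tested.
- **8.7:** "95% confidence intervals will be calculated for all means". No interval is planned for a proportion or for a difference in proportions.
- **8.8.3:** supplemental analyses are marked as not applicable.

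The non-inferiority aim appears only in 8.1. The synopsis states the primary objective as determining how effective OptiClose is, and names neither hypothesis. No section states a non-inferiority margin.

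**The concern.** A non-inferiority purpose needs a margin and a confidence limit to set against it. The plan has neither for its primary endpoint. A test of difference addresses another question: whether the data are hard to reconcile with equal rates. In a small trial with few failures, such a test is often non-significant even when one product is materially worse.

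The switching sentence adds a second problem. It abandons the stated hypothesis because of results that are not described, for an endpoint that is not named. If the plan is followed, a neutral result leaves no rule by which the 8.1 purpose has been met or missed, and nothing stops a non-significant p-value from being offered as support for OptiClose. The 90% power quoted in the same paragraph could also be taken to cover the primary endpoint, which it does not.

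**Working it through.** **Inputs from the documents.** 15 per product in each length group, hence 30 per product if pooled; 60 in all; dry-time SD 0.01 in each group; one-sided alpha 0.025; power 90%; stated detectable difference 0.02226. **Assumptions, not in the documents:** every failure rate and margin below, and a two-sided 5% level for the chi-square (8.8.1 gives none). The chi-square is used without continuity correction.

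**1. The plan's own figure.** For n = 15 per product the normal approximation gives 0.01 × √(2/15) × (1.960 + 1.282) = 0.01184, and the noncentral t gives 0.01226. The stated 0.02226 is not reproduced. It exceeds the t value by 0.0100, which would fit either an unstated margin of 0.01 or a digit error; the text supports neither over the other. In any case the figure concerns dry time. No power or precision is given for wound apposition.

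**2. A neutral chi-square alongside a large possible deficit.** Take success in 12/15 (OptiClose) against 15/15 (Dermabond).
- Pooled success is 27/30 = 0.9. The standard error is √(0.9 × 0.1 × 2/15) = 0.1095, so z = 0.2/0.1095 = 1.826, chi-square = 3.33 and p = 0.068.
- Wilson limits are 0.548 to 0.930 and 0.796 to 1.000.
- Newcombe lower limit: -0.2 - √((0.8 - 0.548)² + 0²) = -0.452.
- Newcombe upper limit: -0.2 + √((0.930 - 0.8)² + (1 - 0.796)²) = +0.042.

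The test finds no significant difference, while the interval runs from -45 to +4 points.

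**3. Best possible data.** With no failures on either product the Newcombe limit is z²/(n + z²):
- 30 v 30: 3.841/33.841 = 11.4 points.
- 15 v 15: 3.841/18.841 = 20.4 points.

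The chi-square statistic cannot be computed here, because the expected failure counts are zero.

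**4. Chance of missing a real deficit.** Exact binomial enumeration with failure rates of 20% (OptiClose) and 3% (Dermabond) gives chi-square power of 0.608 (30 v 30) and 0.242 (15 v 15). The test is therefore non-significant in 39% and 76% of trials.

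**5. Chance of showing non-inferiority when the products are equal.** This sums the binomial probabilities of all outcomes whose unstratified 95% Newcombe interval excludes the margin. At 3% failure on both products and a 10-point margin the result is 0.263 (30 v 30) and 0.046 (15 v 15). Ranges over common failure rates of 1%, 3%, 5% and 10%:

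| Assumed margin | 30 v 30 | 15 v 15 |
|---|---|---|
| 5 points | 0–7% | 0–4% |
| 10 points | 18–26% | 1–11% |
| 15 points | 41–80% | 12–26% |
| 20 points | 68–97% | 12–34% |

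**6. If the sentence in 8.1 refers to trial data.** Let the interval be for OptiClose minus Dermabond success and the margin be -M. Indeterminate means that the interval straddles -M, so its lower limit is below zero. On the same endpoint and confidence level, OptiClose superiority is then already excluded. A matching difference test can be neutral, or significant against OptiClose. An example of the latter is 5/30 v 0/30 failures: chi-square = 5.45, p = 0.020, with an interval of -33.6 to -2.0 points, which is indeterminate at a 10-point margin. Under the 20% v 3% assumption, about 53% of pooled trials and 20% of 15 v 15 trials fall in this class.

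**The case against.** Four points can be made for the plan.

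- **The sentence may have nothing to do with outcome data.** It stands in the sample-size section, the text around it is in the future tense, and the excess of 0.0100 found in step 1 would fit a software run for superiority by a margin. A reader might infer that the hypothesis was changed after non-inferiority failed on trial data. The documents do not support that: the version history gives two dates and does not say that data had been seen. This stands, and the point does not depend on that reading. On either reading the margin and the primary interval are missing.
- **A difference test can sometimes show non-inferiority.** A significant result in favour of OptiClose would imply it at any margin. So it is too strong to say that the chi-square can never do so. The gap concerns neutral results, which are the ones a non-inferiority aim has to be able to interpret.
- **Non-inferiority may not be the real aim.** It appears only in 8.1, and the synopsis objective is broader. This stands too, and it makes aligning 8.1 with the synopsis a legitimate repair.
- **Misuse of a neutral result is not shown.** A reader might infer that a non-significant p-value will be presented as equivalence. No section says so. The plan merely fails to prevent it.

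The numerical illustrations rest on assumed rates and margins, and with a 20-point margin and pooled groups the prospects are fair (68–97%).

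**Conclusion.** Wrong as written, and it should be fixed before any conclusion is drawn. Section 8.1 contradicts itself on the hypothesis, no margin is stated, and 8.7 and 8.8.1 together leave the primary proportion without a confidence interval. These findings need no assumed figures. As planned, a neutral primary result cannot support the purpose stated in 8.1, and the 90% power says nothing about it.

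The size depends on assumptions. Even failure-free data leave a deficit of up to 11.4 points (pooled) or 20.4 points (one length group) unexcluded. At an assumed 10-point margin with 3% failure on both products, the chance of showing non-inferiority is about 26% or 5%.

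A reader might go further and conclude that, after an indeterminate non-inferiority result, the switch could only end in a non-significant p-value. That is not so: the test could also be significant against OptiClose. The exclusion of OptiClose superiority holds only if the sentence means trial data and the endpoint and confidence level are the same. Section 8.1 settles neither.

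**What to change.** 1. **8.1:** delete the switching sentence. State that the 90% power applies to dry time only, and give the expected width of the interval for the primary endpoint.
2. **8.8.1:** make the primary analysis the difference in success proportion, OptiClose minus Dermabond, with a 95% score-type interval (for example Miettinen-Nurminen) stratified by incision-length group. State that a non-significant difference is not evidence of non-inferiority.
3. **Margin:** if one was fixed before data were seen, state it in 8.1 and compare the interval with it. Otherwise drop the non-inferiority claim, align 8.1 with the synopsis objective, and report the estimate and interval.
4. **If a non-inferiority analysis of trial data has already been done:** report it first, as non-inferiority not shown, and label the superiority test post hoc.

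The cost is wording and one interval. The conclusion allowed becomes less favourable. These changes make the report honest but do not make non-inferiority attainable: with 60 participants it is unlikely to be shown at a tight margin, and the realistic result is an estimate with a wide interval. The illustrations above use unstratified Newcombe intervals, so the figures for the stratified interval should be computed when 8.1 is revised.

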**Phase:**

**Objectives:** *Primary objective:* To determine the effectiveness of the OptiClose surgical adhesive.

*Secondary Objective(s):* Secondary outcomes include:

- The incidence of any surgical site infections (SSI).
- The incidence and extent of acute inflammatory reactions is documented by

the International Contact Dermatitis Research Group (ICDRG) grading system following application until second follow up visit.

- Optimal cosmesis score (Modified Hollander Score)
- Application/Dry time - liquid adhesive is no longer wet to the touch.
- Number of applicator tubes used of each product

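### The trial is sized only on dry time, and the binary primary endpoint is to be judged by a p-value alone, with no stated power, precision or confidence interval

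*Combined protocol and SAP*

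**What the plan says.** The synopsis gives the primary objective as "To determine the effectiveness of the OptiClose surgical adhesive". The endpoint, repeated in section 8.8.1, is the incidence of apposition without dehiscence or need for re-approximation, so each participant either succeeds or fails.

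Section 8.1 holds the only sample-size calculation: "A sample size of 30 per incisional length group was estimated based on the secondary outcome of difference in mean “Dry Time". "The comparison will be made using a one-sided, two-sample unequal-variance t-test", at a type I error of 0.025. It also says "The standard deviation for Group 1 is assumed to be 0.01 and the standard deviation for Group 2 is assumed to be 0.01", and it reports 90% power for a detectable difference in means of 0.02226 with 15 participants per product. The same section gives non-inferiority as the purpose of the study, then says that superiority results are being reported because the non-inferiority results were indeterminate.

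Section 8.2 sets 15 participants per product within each incision-length group, 60 in all. For the primary endpoint, section 8.8.1 specifies a chi-square test and ends: "The p-value will be obtained to determine the statistical significance of the observed difference". It gives no significance level, sidedness, expected rate or margin, and does not say whether the length groups are pooled. On intervals, section 8.7 says only: "95% confidence intervals will be calculated for all means".

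**The concern.** The sizing calculation and the primary analysis differ in outcome, scale and test. No wound-failure rate or difference enters 8.1, so nothing there tells the reader what 60 participants can show about wound closure.

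The analysis section does not fill the gap. A bare p-value above 0.05 from a small binary comparison is compatible both with equal performance and with a materially worse product. Section 2.3.3 expects the study to help validate OptiClose's durability, and 8.1 states a non-inferiority purpose. In that setting a non-significant p-value is easily read as showing that the products perform equally, and no planned output would show how large a disadvantage the data still allow.

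**Working it through.** **1. The plan's own figure.** Inputs from 8.1: SD 0.01 per group, 15 per product, one-sided 0.025. The standard error is 0.01 × √(2/15) = 0.003651. The printed difference of 0.02226 gives a noncentrality of 0.02226/0.003651 = 6.10, and the noncentral t with 28 df gives power above 99.99%. Power of 90% corresponds to a difference of 0.01226. The printed 90% is therefore not reproduced even for dry time. That needs its own correction. Here it matters only because the 90% should not be restated as it stands.

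**2. What the chi-square needs, with no assumed rates.** For 0 failures of n on one product and j of n on the other, the uncorrected Pearson statistic reduces to 2nj/(2n − j).

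| Failures | 15 v 15 | 30 v 30 |
|---|---|---|
| 0 v 3 | 90/27 = 3.33, p = 0.068 | 180/57 = 3.16, p = 0.076 |
| 0 v 4 | 120/26 = 4.62, p = 0.032 | 240/56 = 4.29, p = 0.038 |

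Three failures against none is non-significant at either size. Within a length group that is 20% against 0%.

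**3. Power for the primary comparison.** The documents give no failure rates, so those below are assumptions. The method sums the binomial probabilities of every 2×2 table that the uncorrected Pearson test rejects at two-sided 0.05. That level is also assumed, since 8.8.1 states none.

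| Assumed failure rates | 15 v 15 | 30 v 30 pooled |
|---|---|---|
| 2% v 5% | 0.4% | 3.5% |
| 5% v 10% | 2.8% | 10.6% |
| 5% v 15% | 8.9% | 26.4% |
| 5% v 20% | 18.8% | 45.3% |
| 5% v 30% | 44.6% | 77.8% |

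Fisher's exact test gives less. At 30 v 30 it has 9.3% for 5% v 15% and 24.1% for 5% v 20%.

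**4. What an interval would show.** Newcombe's interval combines the Wilson limits for each arm.

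- *1/30 v 1/30.* With z² = 3.8415, the Wilson centre is (0.0333 + 0.0640)/1.1280 = 0.0863 and the half-width is 0.0804, so the limits are 0.0059 and 0.1667. The half-width for the difference is √[(0.0333 − 0.0059)² + (0.1667 − 0.0333)²] = 0.136. The interval is −13.6 to +13.6 points.
- *0/30 v 0/30.* The Wilson limits are 0 and 0.1135, so the interval is −11.4 to +11.4 points.
- *3/30 v 0/30.* The Wilson limits for 3/30 are 0.0346 and 0.2562. The lower limit for the difference is 0.10 − √[(0.10 − 0.0346)² + 0.1135²] = −0.031. The upper limit is 0.10 + (0.2562 − 0.10) = 0.256. The p-value of 0.076 would be reported alone, while the interval for excess failure runs from about −3 to +26 points.

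**The case against.** The strongest reply is that the plan is open about its basis. Section 8.1 calls dry time a secondary outcome and ties the 90% to a difference in means at 15 v 15. A reader might infer that the plan overstates its power for the primary endpoint. It does not, because it makes no power claim for that endpoint. The fault is an omission.

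A reader might also infer from the low powers that a non-significant primary result is almost certain. That does not follow. The documents give no failure rates, and within the range tabulated pooled power reaches 45% at 5% v 20% and 78% at 5% v 30%. The figures also depend on the test variant, the significance level and pooling, none of which 8.8.1 fixes.

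Nor does the interval sentence in 8.7 bar an interval for proportions. It simply does not promise one. Counts and percentages will be reported, so a reader could compute an interval afterwards.

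Finally, no non-inferiority margin is given, so an interval alone cannot settle non-inferiority.

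All of this stands, and it limits how strongly the point can be put. It does not supply the missing statement of precision, and it does not make a p-value an adequate primary result. An interval that readers must work out for themselves is not a prespecified one.

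**Conclusion.** The point holds as an omission in sizing and a weakness in the planned analysis. N of 60 was chosen for mean dry time. The documents state no power or precision for the primary endpoint, and the primary result is planned as a p-value with no interval.

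The size depends on assumed rates: power of about 26% pooled and 9% within a length group for 5% v 15% failure, and about 45% and 19% for 5% v 20%. One failure in 30 on each product leaves differences of up to about 14 points in either direction open.

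These figures rest on uncorrected Pearson at two-sided 0.05 and on intervals that ignore the length strata. They also read the 8.8.1 test as a comparison of primary-endpoint failures. Its text says the chi-square compares adverse events, which should be reconciled with the endpoint named above it.

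**What to change.** Keep N at 60.

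- **8.8.1.** Make the primary result the OptiClose minus Dermabond difference in the proportion with intact apposition, with a 95% score-type interval stratified by incision-length group (for example stratified Miettinen-Nurminen or stratified Newcombe). Report the p-value as supportive.
- **8.7.** Extend the interval sentence to this difference.
- **Interpretation.** State that a non-significant p-value will not be reported as equal effectiveness, and that the conclusion will quote the interval limit unfavourable to OptiClose.
- **Timing.** The past tense about non-inferiority results in 8.1 suggests that results may have been known when the text was written. If they were known when the interval is added, label it post hoc.
- **8.1.** Add one sentence saying that N was not chosen for the primary endpoint, with the expected interval width under stated assumptions (for example, about ±14 points at 1/30 v 1/30, unstratified). Do not reaffirm the dry-time 90% until the 0.02226 figure has been corrected separately.

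The cost is wording in three sections and one extra interval to program, with no added participants, visits or data. The drawback is that the stated precision for the primary question will look much less favourable.
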